1.0 Introduction

This Statistical Analysis Plan (SAP) describes the statistical analyses for AGN-151586 Study M21-500: A Phase 3, Multicenter Study to Evaluate the Safety and Efficacy of AGN-151586 for the Treatment of Glabellar Lines.

Study M21-500 examines the safety and efficacy of AGN-151586 (containing botulinum toxin type E) for treatment in subjects with moderate to severe glabellar lines.

The SAP will not be updated in case of administrative changes or amendments to the protocol unless the changes impact the analysis.

Unless noted otherwise, all analyses will be performed using SAS Version 9.4 (SAS Institute Inc., Cary, NC 27513) or later under the Linux operating system.

This SAP includes changes to analyses described in the protocol. Details are outlined in Section [14.0](#).

2.0 Study Design and Objectives

2.1 Objectives, Hypotheses and Estimands

The study objective is to evaluate the safety and efficacy of AGN-151586 for the treatment of glabellar lines (GL) in subjects with moderate to severe GL.

The clinical hypothesis is that AGN-151586 is more effective than placebo in treating GL, as measured by both investigator and subject assessment of GL severity at maximum frown using the Facial Wrinkle Scale (FWS), and that it has an acceptable safety profile after single and repeat treatments.

Estimands: Primary Endpoints

The attributes of the estimands corresponding to the primary and coprimary efficacy endpoints are summarized in [Table 1](#) (see Section [9.3.2](#)). In addition, the attribute of treatment is a single dose of AGN-151586 or placebo.

For the US FDA, the estimand for the primary composite endpoint is defined as follows:

- Difference in the proportion of subjects who would achieve a Grade 0 or 1 (none or mild) and at least a 2-grade improvement from baseline in composite FWS (as assessed by both investigator and by subject) at Day 7 had they not missed FWS assessments, for the AGN-151586 group in comparison with placebo in the ITT population

For EU Regulatory Agencies, the estimands for the coprimary endpoints are defined as follows:

- Difference in the proportion of subjects who would achieve \geq 2-grade improvement from baseline in FWS as assessed by investigator at Day 7 had they not missed FWS assessments, for the AGN-151586 group in comparison with placebo in the ITT population, and
- Difference in the proportion of subjects who would achieve \geq 2-grade improvement from baseline in FWS as assessed by subject at Day 7 had they not missed FWS assessments, for the AGN-151586 group in comparison with placebo in the ITT population

Any missing assessments will be assumed to be missing at random and imputed using multiple imputation. Statistical significance of the difference will be tested using Cochran-Mantel-Haenszel (CMH) test [REDACTED]
[REDACTED].

Estimands: Secondary Endpoints

The attributes of the estimands corresponding to the secondary efficacy endpoints are summarized in [Table 2](#) (see Section 9.4.2). Treatment is the same as for the primary efficacy endpoints. For both US FDA and EU variables/endpoints, the population is the ITT population (all randomized). For the EU, subgroup analyses will be performed for the coprimary and key secondary endpoints for the ITT population that also has baseline 11-item Facial Line Outcomes (FLO-11) total scores (transformed) \leq 50. The

variables/endpoints listed have the same handling of intercurrent events and statistical summary (including population-level summary and analysis methods) within their respective analysis populations for the US FDA and EU, per estimand label.

2.2 Study Design Overview

The schematic of the study is shown in [Figure 1](#) for this study for the double-blind (DB) period and the open-label (OL) period.

2.3 Treatment Assignment and Blinding

Subjects will be randomized to AGN-151586 [REDACTED] or placebo in a 3:1 ratio.

2.4 Sample Size Determination

Approximately 600 subjects will be randomized into the study in a 3:1 ratio, yielding approximately 450 subjects in the AGN-151586 group and 150 subjects in the placebo group in the treatment period.

For the US FDA, a sample size of 600 subjects will have > 99% power to detect a difference on Day 7 between the AGN-151586 group and the placebo group using the composite endpoint of \geq 2-grade improvement, [REDACTED]

For the EU regulatory agencies, a sample size of 600 subjects for the ITT population will have >99% power (and the subgroup population of an estimated 360 subjects will provide > 99% power) to detect a difference between the AGN-151586 group and the placebo group at Day 7 for each of the coprimary endpoints, [REDACTED]

Sample size calculations were based on the two group χ^2 two-sided test of equal proportions using nQuery (Version 7.0) at a 0.05 level of significance.

3.0 Endpoints

3.1 Primary Endpoints

For the FDA, the primary composite endpoint is the achievement of a Grade 0 or 1 (none or mild) and at least a 2-grade improvement from baseline on the FWS according to both investigator and subject assessments of GL severity using FWS at maximum frown at Day 7.

For EU regulatory agencies, the coprimary endpoints are the achievement of at least a 2-grade improvement from baseline on the FWS according to: (1) subject assessment of GL severity at maximum frown at Day 7, and (2) investigator assessment of GL severity using FWS at maximum frown at Day 7.

3.2 Secondary Endpoints

For US FDA:

- Key secondary endpoint: a Grade 0 or 1 (none or mild) and at least a 2-grade improvement from baseline on the FWS according to both investigator and subject assessments (i.e., concurrent composite) of GL severity at maximum frown over time (DB period)*
- Key secondary endpoint: a Grade 0 or 1 (none or mild) and at least a 2-grade improvement from baseline on the FWS according to investigator assessment of GL severity at maximum frown over time (DB period)*
- Key secondary endpoint: a Grade 0 or 1 (none or mild) and at least a 2-grade improvement from baseline on the FWS according to subject assessment of GL severity at maximum frown over time (DB period)*
- *Mostly satisfied* or *Very satisfied* on the FLSQ follow-up version Item 5 (*overall satisfaction*) for GL at Day 7
- *Mostly satisfied* or *Very satisfied* on the FLSQ follow-up version Item 5 (*overall satisfaction*) for GL at Hour 24
- *Mostly satisfied* or *Very satisfied* on the FLSQ follow-up version Item 4 (*natural look*) for GL at Day 7

For EU regulatory agencies:

- Key secondary endpoint: \geq 20-point improvement from baseline in FLO-11 total scores for GL at Day 7
- \geq 2-grade improvement from baseline on the FWS according to subject assessment of GL severity at maximum frown at Hour 24

- \geq 2-grade improvement from baseline on the FWS according to investigator assessment of GL severity at maximum frown at Hour 24
- \geq 1-grade improvement from baseline on the FWS according to subject assessment of GL severity at maximum frown at Hour 24
- \geq 1-grade improvement from baseline on the FWS according to investigator assessment of GL severity at maximum frown at Hour 24
- *Mostly satisfied* or *Very satisfied* on the FLSQ follow-up version Item 5 (overall satisfaction) for GL at Hour 24
- *Mostly satisfied* or *Very satisfied* on the FLSQ follow-up version Item 4 (natural look) for GL at Day 7
- Time to the first \geq 1-grade improvement from baseline on the FWS according to subject assessment of GL severity at maximum frown over time (DB period)*
- Time to the first \geq 1-grade improvement from baseline on the FWS according to investigator assessment of GL severity at maximum frown over time (DB period)*
- \geq 2-grade improvement from baseline on the FWS according to subject assessment of GL severity at maximum frown over time (DB period)*
- \geq 2-grade improvement from baseline on the FWS according to investigator assessment of GL severity at maximum frown at over time (DB period)*
- Time to return to baseline FWS criterion[†] according to subject assessment of FWS at maximum frown (DB period)*
- Time to return to baseline FWS criterion[†] according to investigator assessment of FWS at maximum frown (DB period)*
- *Mostly satisfied* or *Very satisfied* on the FLSQ follow-up version Item 5 (overall satisfaction) for GL over time*
- \geq 4-point improvement from baseline in FLO-11 Item 10 (look angry) for GL at Day 7
- \geq 4-point improvement from baseline in FLO-11 Item 5 (look less attractive) for GL at Day 7
- Subject-reported global assessment of change in GL based on the Global Assessment of Change in Glabellar Lines (GAC-GL) over time*

* Endpoints will be excluded from hierarchical testing.

3.3 Other Efficacy Endpoints

The primary and secondary efficacy endpoints are listed in Section 3.1 and Section 3.2, respectively. For both the US FDA and EU regulatory agencies, analyses for additional efficacy endpoints will be performed on the ITT population. The additional efficacy endpoints are as follows:

[REDACTED]

[REDACTED]

[REDACTED]

[REDACTED]

3.4 Safety Endpoints

The safety endpoints are the incidence of AEs for the entire study population, change from baseline in vital signs parameters, change from baseline in electrocardiogram (ECG) parameters, change from baseline in laboratory evaluations (hematology and chemistry), and presence of binding and neutralizing antidrug antibodies. Results of a neurological assessment (which includes assessment of cranial nerves II through VII) will be reviewed as an additional safety measure. After the screening visit, clinically significant (as per investigator) neurological assessment abnormalities (or worsening of a baseline condition) will be captured as AEs.

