- c. ≥ 2-grade improvement from baseline on the FWS according to **investigator assessment** of GL severity at maximum frown at Hour 24
- d. ≥ 1-grade improvement from baseline on the FWS according to subject assessment of GL severity at maximum frown at Hour 24
- e. ≥ 1-grade improvement from baseline on the FWS according to **investigator assessment** of GL severity at maximum frown at Hour 24
- f. *Mostly satisfied* or *Very satisfied* on the FLSQ follow-up version Item 5 (overall satisfaction) for GL at Hour 24
- g. *Mostly satisfied or Very satisfied* on the FLSQ follow-up version Item 4 (natural look) for GL at Day 7
- h. Time to the first ≥ 1-grade improvement from baseline on the FWS according to **subject assessments** of GL severity at maximum frown (double-blind period)*
- i. Time to the first ≥ 1-grade improvement from baseline on the FWS according to investigator assessments of GL severity at maximum frown (double-blind period)*
- j. ≥ 2-grade improvement from baseline on the FWS according to subject assessments of GL severity at maximum frown over time (double-blind period)*
- k. ≥ 2-grade improvement from baseline on the FWS according to investigator assessments of GL severity at maximum frown over time (double-blind period)*
- I. Time to return to baseline FWS according to subject assessments of FWS at maximum frown (double-blind period)*
- m. Time to return to baseline FWS according to investigator assessments of FWS at maximum frown (double-blind period)*
- n. Mostly satisfied or Very satisfied on the FLSQ follow-up version Item 5 (overall satisfaction) for GL over time*
- o. ≥ 4-point improvement from baseline in FLO-11 Item 10 (look angry) for GL at Day 7
- p. ≥ 4-point improvement from baseline in FLO-11 Item 5 (look less attractive) for GL at Day 7
- g. Subject-reported global assessment of change in GL based on

	the Global Assessment of Change in Glabellar Lines (GAC-GL) over time*	
	* Endpoints will be excluded from hierarchical testing	
	Safety Endpoints:	
	 Incidence of adverse events (including any abnormality found during neurological assessment and physical examination) 	
	Change from baseline in vital sign parameters	
	Change from baseline in ECG parameters	
	 Change from baseline in laboratory evaluations (hematology and chemistry) 	
	Presence of binding and neutralizing antidrug antibodies	
Investigators:	Multicenter	
Study Sites:	Approximately 38 sites	

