3.5 Safety Endpoints

Safety evaluations include adverse event (AE) monitoring, vital sign measurements, 12-lead electrocardiogram (ECG) collection, laboratory evaluations (hematology and chemistry), neurological assessment (examination to consist of assessment of cranial nerves II through VII), and physical examinations as measures of safety. The safety endpoints are:

- Incidence of AEs (including any abnormality found during neurological assessment and physical examination)
- Change from baseline in vital sign parameters
- Change from baseline in ECG parameters
- Change from baseline in laboratory evaluations (hematology and chemistry)
- Presence of binding and neutralizing antidrug antibodies (see Section 3.6 for more details)

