7.5 Statistical Analyses for Safety

The safety analyses will be performed using the safety population (i.e., Safety Analysis Set). The safety parameters will include AEs, vital sign measurements, 12-lead ECG, laboratory evaluations (hematology and chemistry), neurological assessment (examination to consist of assessment of cranial nerves II through VII), physical examination, and immunogenicity. The last nonmissing safety assessment before study drug administration will be used as the baseline for all analyses of that endpoint.

Treatment-emergent AEs are defined as any AE with the onset that is after the first dose of study drug. Events where the onset date is the same as the study drug start date are assumed to be treatment-emergent, unless known to have started prior to study treatment administration.

An overview of AEs will be presented consisting of the number and percentage of subjects experiencing at least one event for each of the following AE categories:

- 1. Any TEAE
- 2. Any TEAE related to study treatment according to the investigator (i.e., study drug-related, study injection procedure-related)
- 3. Any severe TEAE
 - a. Any severe TEAE related to study treatment according to the investigator
- 4. Any serious TEAE
 - a. Any serious TEAE related to study treatment according to the investigator
- 5. Any TEAE leading to discontinuation of study drug
- 6. Any TEAE leading to death
- 7. PDSOT TEAEs
- 8. Neurological assessment TEAEs
- 9. All deaths

Treatment-emergent AEs will be summarized by system organ class (SOC) and PT; by maximum relationship to study treatment (i.e., study drug related, study injection procedure related) as assessed by the investigator (e.g., reasonable possibility or no reasonable possibility) and SOC and PT; by maximum severity and SOC and PT; and by subject number and SOC and PT. Specific treatment-emergent AEs will be counted once for each subject for calculating percentages, unless stated otherwise. In addition, if the same AE occurs multiple times within a subject, the AE will be counted only once, and the highest severity and level of relationship to investigational product will be reported.

Serious AEs (including deaths) and AEs leading to study drug discontinuation will be summarized by SOC and PT and in listing format.

Possible distant spread of toxin PTs will be identified in the SAP and PDSOT TEAEs will be summarized by PT.

Neurological assessment TEAEs will be summarized by PT.

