10.0 Safety Analyses

10.1 General Considerations

Safety data will be summarized for the Safety Population. Safety summaries will be presented by treatment group, by overall study, by study period, and by treatments received in the DB Period and in the OL Period (i.e., AGN-151586/AGN-151586, AGN-151586/None, Placebo/AGN-151586, Placebo/None).

For the safety analysis, subjects are assigned to a treatment group based on the treatment actually received, regardless of the treatment randomized.

The safety parameters will include AEs, vital signs, 12-lead ECGs, laboratory evaluations (hematology and chemistry), neurological assessment (including examination of cranial nerves II through VII), and presence of antidrug antibodies. For change from baseline safety parameters, “baseline” refers to the last non-missing observation before the first study drug administration in the study.

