10.2.7 Neurological Assessment Adverse Events

The neurological assessment, which is comprised of a Focused Symptoms Questionnaire and a Focused Neurological Examination, will be conducted at selected study visits per protocol. Neurological assessment-associated TEAEs will be summarized by PT. The PTs will be based on the current MedDRA version prior to database lock.

Tables and listings of AEs related to the neurological assessment will be provided.

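### The SAP narrows the protocol's adverse-event endpoint: unless reported as AEs, neurological abnormalities judged not clinically significant, and physical-examination abnormalities, have no visible planned table

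*SAP*

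**What the plan says.** The protocol states the endpoint twice in matching terms: "Incidence of adverse events (including any abnormality found during neurological assessment and physical examination" in the Synopsis and "Incidence of AEs (including any abnormality found during neurological assessment and physical examination" in Section 3.5. Protocol 7.5 ends its list of safety parameters with "neurological assessment (examination to consist of assessment of cranial nerves II through VII), physical examination, and immunogenicity".

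SAP 3.4 opens with "The safety endpoints are the incidence of AEs for the entire study population" and does not carry over the clause about examination abnormalities. It says that results of the neurological assessment "will be reviewed as an additional safety measure" and that, after screening, "clinically significant (as per investigator) neurological assessment abnormalities (or worsening of a baseline condition) will be captured as AEs". The SAP 10.1 parameter list ends with "neurological assessment (including examination of cranial nerves II through VII), and presence of antidrug antibodies"; physical examination is not in it.

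For output, SAP 10.2.7 describes the assessment as a symptom questionnaire plus a focused examination. It then plans AE summaries: "Neurological assessment-associated TEAEs will be summarized by PT", with supporting AE tables and listings. SAP 1.0 says that the SAP changes some protocol analyses and sends the reader to Section 14.0 for the details.

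**The concern.** The protocol makes an examination finding part of the endpoint because it was found. The SAP makes a neurological finding part of the endpoint when the investigator calls it clinically significant or when a baseline condition has worsened. These are different counts, and the SAP's is the narrower.

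What is at stake is visibility. Laboratory values, vital signs and ECG each have change-from-baseline summaries and counts of potentially clinically important values (SAP 10.3, 10.4, 10.6), none of which needs an AE report. The neurological assessment has only AE-based output. Yet it covers cranial nerves II to VII, and Protocol 2.2 names eyelid ptosis, facial paresis and muscular weakness among the reactions that may occur. No AEs of special interest are defined (Protocol 6.1) and there is no data monitoring committee, so the planned tables are the main place where such findings would be seen.

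**Working it through.** Neither document states a figure for this point, so there is none to reproduce. The check is a comparison of texts, followed by an illustration on assumed rates.

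**Texts side by side**

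| Item | Protocol | SAP |
|---|---|---|
| Neurological finding in the AE endpoint | Any abnormality (Synopsis, 3.5) | Clinically significant per investigator, or worsening of a baseline condition (3.4) |
| Physical-examination finding in the AE endpoint | Any abnormality (Synopsis, 3.5) | Not mentioned (3.4) |
| Physical examination as a safety parameter | Listed (7.5) | Not listed (10.1) |
| Planned neurological output | TEAEs by preferred term (7.5) | TEAEs by preferred term, AE tables and listings (10.2.7) |
| Record of the change | – | No visible entry (14.0, partly redacted) |

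**Is the filter already in the protocol?** Protocol 6.1 limits when a finding counts as an AE only for laboratory abnormalities and vital-sign changes. It sets no such limit for neurological or physical findings, so the SAP filter is new. The only visible entry on the subject in SAP 14.0, under version 2.0, records that neurological safety assessments were added.

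**Which findings have no table?**
1. A finding judged clinically significant, or a worsened baseline condition, becomes an AE and reaches the TEAE tables.
2. A finding reported under the general AE definition in Protocol 6.1 also reaches them, whichever examination revealed it.
3. The possible distant spread of toxin (PDSOT) table (SAP 10.2.6) also counts reported TEAEs, so it cannot recover a finding never reported as an AE.
4. What remains is new neurological abnormalities judged not clinically significant, and physical-examination abnormalities, in both cases when no AE is reported.

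**Illustration on assumed rates.** Let p be the share of active subjects with a new examination abnormality and f the share of those tabulated by any route. Neither is in the documents. With about 450 active subjects (SAP 2.4), tabulated = 450 × p × f and missing = 450 × p × (1 − f).

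| p | With a finding | f = 1: tabulated / missing | f = 0.5 | f = 0.25 | f = 0 |
|---|---|---|---|---|---|
| 1% | 4.5 | 4.5 / 0 | 2.25 / 2.25 | 1.1 / 3.4 | 0 / 4.5 |
| 5% | 22.5 | 22.5 / 0 | 11.25 / 11.25 | 5.6 / 16.9 | 0 / 22.5 |

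The tabulated difference between arms is p₁f₁ − p₀f₀ (1 = active, 0 = placebo). Take p₁ = 5% and p₀ = 1%, a true difference of 4 percentage points:
- f₁ = f₀ = 0.5 gives 2.5 − 0.5 = 2 points.
- f₁ = 0.25, f₀ = 1 gives 1.25 − 1 = 0.25 points.
- f₁ = 1, f₀ = 0 gives 5 − 0 = 5 points.

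The difference can shrink or grow according to how f differs by arm, and the documents do not say how it does.

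**The case against.** The strongest reply is that this is a mismatch of wording with little practical effect. The protocol's endpoint is itself AE incidence, its own analysis section plans neurological TEAEs by preferred term, and SAP 10.2.7 delivers that. SAP 3.4 does not expressly exclude other findings, and the general AE definition in Protocol 6.1, which reaches any unfavourable and unintended sign, is not withdrawn. The Operations Manual and the contents of the activity schedule are not in the public text, and they may hold a capture rule or show that physical examination is not repeated after baseline. Parts of SAP 14.0 are redacted.

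Much of this stands. The protocol asks for no table of examination results, so adding one is a recommendation and goes beyond restoring the protocol. The general definition does leave another route open. But the SAP states one specific rule for neurological findings, that rule is narrower than the endpoint, and the visible text offers nothing to recover what it leaves out.

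Three stronger readings may tempt a reader, and the documents do not support them:
- **That mild signs never reach a safety table.** Clinical significance is not severity. A mild sign reported as an AE appears in the mild TEAE row (SAP 10.2.2), in the neurological TEAE table where it is associated with that assessment, and in the PDSOT table if its preferred term is listed.
- **That signs of toxin spread are lost.** Protocol 6.2 defines distant spread as effects at sites distant from and not adjoining the injection site. Weakness of the lid or brow lies near the glabella.
- **That investigators will dismiss findings mainly in the active arm.** The high Phase 2b response makes it plausible that some could guess the assignment, but nothing shows that they discount such signs. Protocol 2.2 names them as adverse reactions, not as the intended effect. The open-label period has no control group to compare with.

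**Conclusion.** The point holds in a limited form. The SAP's stated rule gives a narrower count than the protocol's safety endpoint, physical examination drops out of the SAP's endpoint and parameter lists, and no visible entry in Section 14.0 reports either change. An under-count of the protocol's endpoint is possible. Its size and its direction by arm cannot be derived from the documents. The illustrated loss runs from none to every such finding, and it is total only if none is judged clinically significant and none is reported as an AE by another route.

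The conclusion assumes that the worsening clause is a separate way into the AE data, that the redacted parts of the SAP contain no examination table or logged change, and that the Operations Manual has no rule restoring the wider capture. It is a discrepancy to reconcile, not evidence of a hidden safety signal.

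**What to change.** 1. In SAP 3.4, restore the protocol's definition so that AE incidence includes any abnormality found at the neurological assessment or physical examination.
2. In SAP 10.1, add physical examination to the safety parameters, to match Protocol 7.5.
3. In SAP 10.2.7, beside the TEAE table, add a descriptive table by treatment group and period. It gives the number and percent of subjects with a new or worsened abnormality at the neurological assessment or at any post-baseline physical examination, regardless of clinical significance or AE reporting. A breakdown by item and visit is optional.
4. Record the revision in SAP 14.0, and check the capture rule against the Operations Manual.

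The cost is some SAP wording and one or two more tables, and some trivial findings will be displayed. The assessments are already planned, but whether results are stored item by item, and whether physical examination is repeated after baseline, could not be checked in the public text.
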